### **Study Design**

Patients enter a one month Screening period to assess inclusion/exclusion criteria, sign informed consent, and determine study eligibility. At the initial screening visit, patients will be instructed in behavior modification techniques to improve IC/BPS symptoms.  Patients are reassessed at least one month later for inclusion/exclusion criteria and determine study eligibility. Patients who do not improve with standard IC/BPS advice and pass clinical and laboratory screening can be participants in the study. Baseline evaluation of the included patients will be done with the O'Leary-Sant Interstitial Cystitis Symptom Index and Problem Index (OSPI). At the baseline visit (week 0), all eligible IC/BPS patients will be randomized in a blinded fashion to receive in a 2:1 ratio either SQ certolizumab pegol 400mg or SQ placebo at weeks 0, 2, 4 followed by a maintenance dose at 8 weeks. The length of the study will be 18 weeks. The effectiveness of certolizumab pegol will be assessed at week 2, 4, 10, and 18 using GRA, ICSI, ICPI, and the numeric pain and urgency scale. After subjective evaluation of efficacy and safety in the initial 30 patients, the total study sample size will be 42 study patients.

A midstream urine will be collected at baseline and weeks 2, 4, 10, and 18 from all participants. Quest Diagnostics Nichols Institute, San Juan Capistrano, CA or similar lab will perform an ELISA TNFα and creatinine levels on these samples.

Pilot Study Evaluating the Efficacy of CZP for Interstitial Cystitis Study Flow Chart

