### **Secondary Outcome Measures**

Improvement in GRA at week 4, 10, and 18

Improvement in the Interstitial Cystitis Symptom Index (ICSI) Interstitial Cystitis Problem Index (ICPI) from baseline to week 2, 4, 10, and 18

11-point numeric pain and urgency scale at baseline, week 2, 4, 10, and 18

Midstream first void urine specimen level of TNF $\alpha$  normalized to urinary creatinine, at week 2,

4, 10, and 18 compared to baseline levels

Adverse events from time of Screening through the last clinic and phone call visit

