# **Estimated enrollment** 42 patients

After subjective evaluation of efficacy and safety in the initial 30 patients, the total study sample size will be 42 study patients.

Previous IC/BPS studies demonstrated an approximate 20% placebo response rate. Monotherapy response rate of certolizumab pegol in rheumatoid arthritis was 45%. To achieve an 80% power using 2:1 randomization and a 2-sided p = .05 a minimum of 39 subjects was required. The sample size was increased by 3 subjects to account for potential participant withdrawals.

Arms	Assigned Intervention					
Group 1: Experimental	Biological: Certolizumab pegol (Cimzia) 400 mg pre-filled syringe loading dose given subcutaneously at week 0, 2, and 4 followed by a maintenance dose at week 8					
Group 2: Placebo Comparator	Placebo: given subcutaneously at week 0, 2, 4, and week 8					

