### **Inclusion Criteria**:

- 1. A diagnosis of IC/BPS defined based on AUA guidelines as the following: an unpleasant sensation (pain, pressure, discomfort) perceived to be related to the urinary bladder, associated with lower urinary tract symptoms of more than 6 months duration, in the absence of infection or identifiable causes, documented history or patient reported.
- 2. Only those patients with moderate to severe IC/BPS will be included in the study.
- 3. Able to provide informed consent to participate in the study and comply with study requirements
- 4. Able to provide written authorization for use and release of health and research study information
- 5. Written documentation of being provided California's Experimental Subject's Bill of Rights
- 6. Females ≥18 and ≤ 65 years of age previously diagnosed with interstitial cystitis/ bladder pain syndrome (IC/BPS) for a duration of greater than 6 months
- 7. Female patients of child-bearing potential must have a negative serum pregnancy test at Screening and use birth control while in the study.
- 8. O'Leary-Sant Interstitial Cystitis Symptom and Problem Indexes (OSPI) score ≥ 18
- 9. No history of any cancer.
- 10. No bacterial cystitis in previous 1 month
- 11. No active herpes in previous 3 months
- 12. Never treated with cyclophosphamide
- 13. No neurogenic bladder dysfunction (due to a spinal cord injury, stroke, Parkinson's disease, multiple sclerosis, spina bifida or diabetic cystopathy)
- 14. Absence of bladder, ureteral or urethral calculi for previous 3 months

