- 19. Other severe acute or chronic medical or psychiatric condition or laboratory abnormality that may increase the risk associated with study participation or investigational product administration or may interfere with the interpretation of study results and, in the judgment of the Investigator, would make the patient inappropriate for entry into this study.

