# **Trial Schedule**

	Screen	>One Month Reevaluation	Baseline	Visit 1	Visits 2, 3	Visit 4	Phone Follow- up 	Phone Follow- up 
Study Day	-37	-7	0	14	28,56	70	98	126
Study Week	-5	-1	0	2	4,8	10	14	18
Study								
procedures:								
Obtain Informed Consent	X							
Medical History	X							
Medication Review	X	X	X	X	X	X		
Vitals 	X	X	X	X	X	X		
Physical Exam	X							
OSPI 	X	X						
anti-HCV, HBsAG		X						
PPD		X						X
CBC						X		X
Urinalysis	X	X	X	X	X	X		
Urine Culture		X	X	X	X	X		
Urine Pregnancy Test		X						
Eligibility Assessment	X	X						
Dispense Study Drug			X	X	X			
Injection Site Evaluation 			X	X	X			
Adverse Events			X	X	X	X	X	X
GRA 				X	X	X		X
ICSI, ICPI 				X	X	X		X
Numeric scale of pain and urgency	X	X	X	X	X	X		X

- 1. Height, weight, blood pressure, pulse, temperature
- 2. O'Leary-Sant Interstitial Cystitis Symptom Index and Problem Index
- 3. Monitor subjects for systemic and local hypersensitivity reactions for one hour after injection

- 4. Global response assessment
- 5. Interstitial Cystitis Symptom Index, Interstitial Cystitis Problem Index
- 6. In-office visit if determined to be clinically necessary

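### The schedule places both blood counts after the last injection and specifies none before the first dose

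*Protocol*

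**What the plan says.** The Protocol makes entry conditional on laboratory results in two places. Study Design admits patients who do not improve with standard advice and who "pass clinical and laboratory screening can be participants in the study". Exclusion 19 bars, at the investigator's judgment, a "laboratory abnormality that may increase the risk associated with study participation or investigational product administration". Neither place names a blood count.

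The Trial Schedule lists tests by visit, with the columns headed "Study Week -5 -1 0 2 4,8 10 14 18". The only blood test marked before dosing is the hepatitis serology row, "anti-HCV, HBsAG", at the week -1 re-evaluation. The CBC row is marked at week 10 and at week 18 and nowhere else.

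Dosing is at weeks 0, 2 and 4, "followed by a maintenance dose at week 8" (treatment arms table). The safety outcome, under Secondary Outcome Measures, is "Adverse events from time of Screening through the last clinic and phone call visit". The SAP does not mention the CBC.

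**The concern.** The plan already considers a CBC worth doing, since it schedules two per patient. Both come after exposure has ended, so the pre-dose value that would make them interpretable is missing. Two things follow for the individual patient.

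- **Eligibility.** The investigator has to decide under exclusion 19 whether a laboratory abnormality raises the risk of receiving a TNF-alpha blocker. If the schedule is followed as written, that decision is taken without a blood count.
- **Reading of safety data.** If a patient has a low count at week 10, the counts alone cannot show whether it arose on study or was there at entry. Adverse events are a listed secondary outcome, and blood problems appear among the stopping criteria, so this attribution is one the trial may have to make.

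The primary endpoint, the other efficacy measures and the sample size do not depend on the CBC. Randomisation also protects a comparison of week-10 counts between arms, but it does not help with one patient's eligibility or one patient's low value.

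**Working it through.** The plan gives no figure to reproduce. The check is a reading of the Trial Schedule by column, followed by a search of both documents for any other mention of a blood count.

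**1. Marks by study day.** The CBC row has all eight visit columns, so each mark can be assigned to a visit.

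| Row | Days marked | Marked at day -7? |
|---|---|---|
| Anti-HCV, HBsAg | -7 | yes |
| PPD | -7, 126 | yes |
| CBC | 70, 126 | no |
| Urinalysis | -37, -7, 0, 14, 28 and 56, 70 | yes |
| Urine culture | -7, 0, 14, 28 and 56, 70 | yes |
| Urine pregnancy test | -7 | yes |
| Study drug dispensed | 0, 14, 28 and 56 | not a test |

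Five of the six test rows have a day -7 mark; CBC is the exception. The PPD row just above it has a before-and-after pair, while CBC has only the after.

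**2. Timing against dosing.**

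- First injection: day 0. Last injection: day 56.
- First CBC: 70 - 56 = 14 days after the last injection, and 70 - 0 = 70 days after the first.
- Second CBC: 126 - 56 = 70 days after the last injection.
- CBCs at or before day 0: 0. CBCs from day 14 to day 56: 0.

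**3. Patients concerned.** With 42 patients at 2:1, 42 × 2/3 = 28 receive active drug. For all 28 no CBC is specified before the first dose. This is a count of patients to whom the gap applies, not an estimate of harm; the documents give no rate of abnormal counts.

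**4. Other text that might supply the test.** CBC appears nowhere else in the available text of the Protocol or SAP. The schedule is not a full list of what is done:

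- Inclusion criterion 7 says that patients of child-bearing potential "must have a negative serum pregnancy test at Screening", and the schedule has no row for that test.
- Study Design says "A midstream urine will be collected at baseline and weeks 2, 4, 10, and 18 from all participants", for TNF-alpha and creatinine, and the schedule has no row for those specimens.

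Both of these tests are nevertheless named in the text. A pre-dose CBC is named neither in the text nor in the schedule.

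**5. Effect of adding one count.** Scheduled CBCs in 42 randomised patients are now 42 × 2 = 84, with 0 before dosing. With one added at day -7 they become 42 × 3 = 126, with 42 before dosing. The interval from day -7 to day 0 leaves 7 days for review.

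**The case against.** The strongest reply is that Study Design already requires laboratory screening and that the schedule does not set out its content. Besides the two tests above, there is no chemistry row, although exclusion 5 bars inadequate renal or hepatic function. On this view a blank in an incomplete table is weak evidence that no CBC is done, and what remains is a panel that was not itemised. This stands in part: an unlisted CBC may well be done. It does not change the fact that the text does not require one.

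A second reply is that the table may be unreliable at this point. The second CBC and second PPD marks sit in a phone follow-up column, which becomes an office visit only if clinically necessary, and neither test can be done by phone. The front pages and the flow chart were not available for this check. A lost or misplaced mark therefore cannot be excluded. Against that, the CBC row has its full column count, and the drug-dispensing row falls on the dosing weeks. The phone-visit placement also makes the week-18 count less certain to be obtained, which weakens any hope of using it in place of a baseline.

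A third reply is that nothing in the plan makes a pre-dose count necessary: no criterion sets a blood-count limit, exclusion 19 is a general clause, and the stopping text on blood problems is symptom-based. That is correct, and it is why the point is minor. Medical history and the week-18 count may help in judging a low week-10 value, but neither replaces a measured baseline.

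**Conclusion.** The concern holds, as a minor point of safety design. The schedule calls for two CBCs per patient, 14 and 70 days after the last injection, and none before the first; no available text in either document specifies a pre-dose count. If the plan is followed as written, exclusion 19 is applied without a blood count, and an individual low count at week 10 has no baseline.

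This rests on the column positions in the schedule being as they appear, and on the front pages and flow chart not naming the test. Confidence is medium for those reasons. If the blank is clerical, or if a CBC is done under the general screening requirement, the remedy is the same and simply records the practice. No probability of an abnormal count is claimed.

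**What to change.** Two edits to the Protocol:

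1. In the Trial Schedule, mark the CBC row at the re-evaluation visit (day -7), on the blood draw already listed for anti-HCV and HBsAg.
2. In Study Design, add one sentence: *Laboratory screening includes a CBC at re-evaluation, reviewed by the investigator under exclusion 19 before randomization at week 0.* The investigator sets the limits.

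The cost is one CBC per re-evaluated patient: 42 for those randomised, plus those who then fail screening, whose number the documents do not give. No new visit or needle-stick is needed. An occasional extra screen failure is possible, at a frequency that cannot be estimated from the documents. No change to the later CBCs is asked for.

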# **Trial Schedule**

	Screen	>One Month Reevaluation	Baseline	Visit 1	Visits 2, 3	Visit 4	Phone Follow- up 	Phone Follow- up 
Study Day	-37	-7	0	14	28,56	70	98	126
Study Week	-5	-1	0	2	4,8	10	14	18
Study								
procedures:								
Obtain Informed Consent	X							
Medical History	X							
Medication Review	X	X	X	X	X	X		
Vitals 	X	X	X	X	X	X		
Physical Exam	X							
OSPI 	X	X						
anti-HCV, HBsAG		X						
PPD		X						X
CBC						X		X
Urinalysis	X	X	X	X	X	X		
Urine Culture		X	X	X	X	X		
Urine Pregnancy Test		X						
Eligibility Assessment	X	X						
Dispense Study Drug			X	X	X			
Injection Site Evaluation 			X	X	X			
Adverse Events			X	X	X	X	X	X
GRA 				X	X	X		X
ICSI, ICPI 				X	X	X		X
Numeric scale of pain and urgency	X	X	X	X	X	X		X

- 1. Height, weight, blood pressure, pulse, temperature
- 2. O'Leary-Sant Interstitial Cystitis Symptom Index and Problem Index
- 3. Monitor subjects for systemic and local hypersensitivity reactions for one hour after injection

- 4. Global response assessment
- 5. Interstitial Cystitis Symptom Index, Interstitial Cystitis Problem Index
- 6. In-office visit if determined to be clinically necessary

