#### **Exclusion criteria:**

- 1. Symptoms are relieved at one month reevaluation visit after receiving IC/BPS behavior modification advice at screening visit.
- 2. Symptoms are relieved by antimicrobials, antibiotics, or other medications for IC/BPS
- 3. Pregnant women, lactating mothers, nursing mothers, women suspected of being pregnant and woman who plan to be pregnant during the course of the clinical trial
- 4. Males
- 5. Patients with inadequate renal, hepatic, or cardiac function
- 6. Patients with history of gross hematuria within 2 years.
- 7. Patients with the following medical history: Lower urinary tract anatomical anomaly, pelvic radiotherapy, or active genital herpes
- 8. Patients with a history of tuberculosis (TB), recent exposure to TB, or recent travel to TB endemic regions. Patients should have a recent negative PPD (or negative CXR) prior to receiving treatment.
- 9. Patients who have undergone cystoscopy under anesthesia with bladder biopsy, hydrodistension, or fulguration of Hunner's ulcer within 3 months
- 10. Patients taking the following treatments for interstitial cystitis at Screening: Intravesical BCG, corticosteroid therapy, cyclosporine, or TNF-alpha inhibitors.
- 11. Patients with a history of receiving live vaccine including Flumist® influenza vaccine in the past 3 months.
- 12. Patients with a history of allergic or anaphylactic reaction to a therapeutic or diagnostic monoclonal antibody or IgG-fusion protein.

[figure not shown]
- 13. Patients with a history of alcohol, analgesic or drug abuse within 2 years of Screening.
- 14. Patients with a history of any cancer.
- 15. Patients with a history of active Hepatitis B, Hepatitis C, or Human Immunodeficiency Virus (HIV) infection, or who are known carriers (Hepatitis B).
- 16. Patients with a history of invasive fungal infections, recent travel to regions endemic for the following invasive fungal infections: San Joaquin Fever, aspergillosis, histoplasmosis, candidiasis, coccidiodomycosis, blastomycosis, and pneumocystosis.
- 17. Patients with a history of diabetes mellitus.
- 18. Patients with a history of a neurologic disease included but not limited to central demyelinating diseases, including multiple sclerosis; and a history of peripheral demyelinating disease, including Guillain-Barre syndrome.

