Statistical Analysis Plan

Pilot Study Evaluating the Efficacy of Certolizumab Pegol for Interstitial

Sample size

Previous IC/BPS studies demonstrated an approximate 20% placebo response rate [29]. Monotherapy response rate of certolizumab pegol in rheumatoid arthritis was 45% [21]. To achieve an 80% power using 2:1 randomization and a 2-sided $p = .05$ a minimum of 39 subjects was required. The sample size was increased by 3 subjects to account for potential participant withdrawals.

Randomization

Eligible participants were computer randomized and received either subcutaneous certolizumab pegol 400gm or placebo (sterile saline) in a 2:1 ratio at weeks 0, 2, 4, and 8. The study drug and placebo were provided in ready to use syringes that were identical other than the blinded ID number on the side of the syringe.

Statistical analysis

Any patient who withdrew from the study, for whatever reason, was classified as a non-responder.

All statistical summaries and 2-sample t-tests were performed using the Data Desk® version 6.3. Comparison of these changes between treatment groups are also shown as 95% confidence intervals (CI). The chi-square test or Fisher's exact test was applied to analyze baseline demographics, improvement with GRA treatment responders, and the proportion of patients with a reduction from baseline of 30% or greater in their pain intensity score between treatment groups.

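### The eligibility criteria require a serum pregnancy test that the Trial Schedule does not list; its only pregnancy test is one urine test at day -7, not repeated at any of the four dosing visits

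*Protocol*

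**What the plan says.** The protocol's Inclusion Criteria, item 7, read: "Female patients of child-bearing potential must have a negative serum pregnancy test at Screening and use birth control while in the study". Exclusion criterion 3 bars pregnant and breast-feeding women and also "women suspected of being pregnant and woman who plan to be pregnant during the course of the clinical trial". It names no test and no time for a retest.

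The Trial Schedule has one pregnancy row, "Urine Pregnancy Test", with a single mark in the re-evaluation column (day -7). The first screening column (day -37) has no pregnancy test, and neither do Baseline, Visit 1 or Visits 2 and 3. Those last three columns are the ones marked in the row "Dispense Study Drug". The arms table gives the active regimen as "400 mg pre-filled syringe loading dose given subcutaneously at week 0, 2, and 4 followed by a maintenance dose at week 8", and Study Design gives the control the same timing: "SQ placebo at weeks 0, 2, 4 followed by a maintenance dose at 8 weeks".

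Study Design admits patients who do not improve on standard advice and who "pass clinical and laboratory screening can be participants in the study". On discontinuation, the SAP says only: "Any patient who withdrew from the study, for whatever reason, was classified as a non-responder".

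**The concern.** There are two separate issues.

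- **Consistency.** The criterion and the schedule name different tests. A site working from the schedule table would run a urine test, and a site working from the criterion would need a blood test that the table does not show. Entry could then rest on different evidence from one woman to the next.
- **Safety.** All participants are women aged 18 to 65, and exclusion 3 shows that the protocol itself aims to avoid pregnancy on study. A pregnancy missed at day -7, or begun later, could be followed by up to four injections with no scheduled test to interrupt them. For the 28 of 42 women allocated to certolizumab pegol under 2:1 randomisation (42 × 2/3 = 28), these would be active drug. The protocol's list of stopping criteria for adverse events does not mention pregnancy.

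The point does not touch sample size, power, type I error or the primary comparison.

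**Working it through.** The plan gives no figure of its own on this point. The check is a comparison of text and table, followed by day counts.

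**1. Test type**

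| Item | Inclusion 7 | Trial Schedule |
|---|---|---|
| Serum test | Required in screening | No row |
| Urine test | Not mentioned | One, at day -7 |
| Test at dosing visits | Not required | None |
| Contraception | Required throughout | No row checks it |

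Study Design describes screening as a period of about a month ending in reassessment, so day -7 can fairly count as screening. The mismatch is therefore in the type of test and not in its date.

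**2. Interval from the only scheduled test to each dose**

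Dose day = week × 7, so weeks 0, 2, 4 and 8 are days 0, 14, 28 and 56. Interval = dose day - (-7):

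- 0 + 7 = 7 days
- 14 + 7 = 21 days
- 28 + 7 = 35 days
- 56 + 7 = 63 days

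**3. What pre-dose tests would change**

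Tests read before each dose divide the 63 days into windows of 7, 14, 14 and 28 days (sum 63). A pregnancy that becomes detectable in the first, second, third or fourth window is caught with 4, 3, 2 or 1 doses still to give. This holds whatever the delay between conception and a positive test.

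**4. Worst-case doses after conception**

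This step needs a detection delay L, which the documents do not give. For each conception day c with c + L later than day -7, count the doses on or after c that precede the first test at or after c + L, and take the maximum over c.

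| Pre-dose tests | Assumed L = 10 to 14 days | Assumed L = 15 to 28 days |
|---|---|---|
| None (current schedule) | 4 | 4 |
| Day 0 only | 4 | not needed |
| Day 0 and Visit 1 | 3 | not needed |
| All four dosing visits | 1 | 2 |

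Example with L = 15: conception on day 0 is detectable from day 15 and found on day 28, after the doses on days 0 and 14. A Baseline test alone leaves the worst case at 4.

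**5. How likely a pregnancy is**

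The documents give no pregnancy rate. Exposure in the active arm is 28 × 63 = 1,764 woman-days, and 1,764 / 365.25 ≈ 4.8 woman-years. At an assumed 1 to 10 pregnancies per 100 woman-years on contraception:

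- All 28 of child-bearing potential: 4.8 × 0.01 ≈ 0.05 to 4.8 × 0.10 ≈ 0.5 expected pregnancies.
- Half of them (assumed): about 0.025 to 0.25.

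The most likely number is zero under any of these values. The counts in step 4 apply only if a pregnancy occurs.

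**The case against.** The strongest case on the other side has five parts.

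- **The schedule is not exhaustive.** It has no row for the urine TNFα and creatinine samples that Study Design requires, and none for renal or hepatic tests although exclusion 5 bars inadequate function. Its eligibility assessment row is marked at both screening visits, and Study Design requires the criteria to be reassessed. A reader might infer that sites would necessarily enrol women without a serum test. The documents do not support that, because inclusion 7 and the eligibility check could prompt a test that the table omits. This stands. What remains is that the table should show a test on which entry depends.
- **The two tests may be cumulative.** Serum in screening followed by urine at day -7 is a possible reading, and the documents do not rule it out. The repair should therefore add the serum test and need not delete the urine one.
- **Women are tested before dosing.** A reader might infer that drug is given with no pregnancy test at all. That is wrong, because the day -7 test precedes all four doses. The gap is the absence of any repeat.
- **Repeat testing is nowhere required.** A reader might infer that the protocol contradicts itself here too. It does not, so this half is an omission. Contraception is mandatory, and dosing visits are in person with medication review. The consent form was not among the documents reviewed, so instructions given there cannot be judged absent. Even so, contraception and self-report depend on adherence and awareness, and no scheduled step verifies them after day -7.
- **The risk is small.** This stands, as step 5 of the working shows. The documents also give no fetal risk for the drug, and none is claimed here.

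**Conclusion.** The point holds in a limited form. Inclusion 7 requires a serum test that the Trial Schedule does not list. The one scheduled pregnancy test, on urine at day -7, is followed by doses 7, 21, 35 and 63 days later with no retest. The first is an inconsistency to correct and the second is a safety gap worth closing. Both rest on the protocol's own text and day counts. Only the worst-case dose counts and the expected number of pregnancies depend on assumed values.

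A reader might also infer that the SAP's non-responder rule already settles how such a woman is analysed. It does not. That rule covers women who leave the study, and one who stops dosing for pregnancy but stays under observation has not left. Her primary outcome will often be in hand, because the week-2 GRA is scheduled at Visit 1 (day 14), before the doses on days 28 and 56.

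The change is worth making because it is cheap, not because an event is probable. Nothing here bears on the efficacy result.

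**What to change.** - **Trial Schedule, screening period.** Add the serum pregnancy test that inclusion 7 requires, drawn with the day -7 blood already needed for hepatitis serology. It may replace the urine test or sit alongside it.
- **Trial Schedule, dosing visits.** For women of child-bearing potential, add a urine pregnancy test at Baseline, Visit 1 and Visits 2 and 3, read before study drug is dispensed. Urine is already collected for urinalysis at each of these visits.
- **Study Design.** Randomise only if the day-0 test is negative. Stop study drug if pregnancy is confirmed, and continue safety follow-up.
- **SAP, Statistical analysis.** State that a woman who stops dosing but remains in follow-up contributes her observed GRA, and that the non-responder rule applies to withdrawal from the study.

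Cost: no new visit. The added urine tests number at most 4 × 42 = 168 if every participant is of child-bearing potential, or 4 × 21 = 84 if half are (assumed). If the serum test is added to the urine test at day -7, there is also one blood assay per eligible woman. The downside is an occasional delayed or cancelled randomisation or dose.
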